**Table 7-1 Clinical Laboratory Tests**

Hematology a	Chemistry b	Coagulation Profile c,d	Serology c	Other e
Hematocrit Hemoglobin Red blood cell (RBC) count White blood cell (WBC) count Neutrophils (%) Lymphocytes (%) Monocytes (%) Basophils (%) Eosinophils (%) Platelet count	Albumin Alanine aminotransaminase (ALT) Aspartate aminotransaminase (AST) Alkaline phosphatase Bilirubin, total Bicarbonate Blood urea nitrogen (BUN) Calcium, total Chloride Creatinine Creatine kinase Glucose Magnesium Phosphorus f Potassium Ca x P j Sodium	Prothrombin time Activated partial thromboplastin time	Hepatitis B infection Hepatitis C infection Human immunodeficiency virus	FSH g Serum pregnancy g FGF-23 h,j Parathyroid Hormone (PTH) c

a Whole blood.

b Serum.

c Plasma.

d Only in people treated with Warfarin.

e Not part of standard clinical laboratory tests, must be specified; performed at specified time points.

f Serum phosphorus is also performed separately from standard clinical laboratory tests at protocol specified time points.

g FSH and serum pregnancy tests are performed on all females at Screening. After screening, pregnancy tests will only be performed on females of child-bearing potential unless FSH at screening indicates post-menopausal status.

h Both intact and c-terminus FGF-23 will be measured.

j Used in efficacy analyses

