**Patient Selection Criteria:**

**Inclusion criteria:**

1. Signed and dated informed consent prior to any study specific procedures.
2. Males or females  $\geq$  18 years of age.
3. Females must be non-pregnant, non-lactating and fulfilling one of the following:
  - a. Post-menopausal defined as amenorrhea for at least 12 months following cessation of all exogenous hormonal treatments and with follicle stimulating hormone (FSH) levels in the laboratory defined post-menopausal range.
  - b. Documentation of irreversible surgical sterilization by hysterectomy, bilateral oophorectomy or bilateral salpingectomy but not tubal ligation.
  - c. Use of acceptable contraceptive method: IUD with spermicide, a female condom with spermicide, contraceptive sponge with spermicide, an intravaginal system (e.g., NuvaRing®), a diaphragm with spermicide, a cervical cap with spermicide, or oral, implantable, transdermal, or injectable contraceptives, sexual abstinence, or a sterile sexual partner.
4. Males must agree to avoid fathering a child (or donating sperm), and therefore be either sterile (documented) or agree to use, from the time of enrollment until 45 days after end of study, one of the following approved methods of contraception: a male condom with

spermicide, a sterile sexual partner, use of an IUD with spermicide by female sexual partner, a female condom with spermicide, contraceptive sponge with spermicide, an intravaginal system (e.g., NuvaRing®), a diaphragm with spermicide, a cervical cap with spermicide, or oral, implantable, transdermal, or injectable contraceptives.

5. Chronic maintenance hemodialysis 3x/week for at least 3 months or chronic maintenance peritoneal dialysis (PD) for a minimum of 6 months. If modality of dialysis has changed, patient must meet one of the two dialysis criteria above and been on the new modality of dialysis for a minimum of one month.
6. Stable vascular access as assessed by Investigator, if on HD.
7.  $Kt/V \geq 1.2$  at most recent measurement prior to screening.
8. Prescribed and taking at least 3 doses of phosphate binder per day. The prescribed dose should have been unchanged during the last 3 weeks prior to screening.
9. Serum phosphorus levels must be between 4.0 and 8.0 mg/dL (inclusive) at screening, analyzed at the central laboratory used in the study.
10. Intentionally left blank.

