### 1.3 Schedule of Events

Study Day	Screening	Washout a			26-Week Treatment Period								
	-21	-14 ±2	-7 ±2	-1 ±2	1	8 ±5	15 ±5	29 ±5	57 ±7	85 ±7	120 ±7	155 ±7	183 ±7
Visit	V1	V2	V3	V4 a	V5 a	V6	V7	V8	V9	V10	V11	V12	V13
Informed consent	X												
Inclusion/Exclusion	X	X	X	X	X								
Demographics	X												
Pre-dialysis Body Weight	X f				X					X			X
Kt/V e	X												
KDQoL/DSF g	X									X			X
Med/Surgical Hx	X	X	X	X	X								
Physical Exam	X				X								X
Vital signs a	X	X	X	X	X	X	X	X	X	X	X	X	X
ECG evaluation	X				X					X			X
Clinical laboratory tests b	X				X					X			X
FSH test c	X												
Pregnancy test c (serum)	X				X					X			X
HIV, hepatitis B and C tests	X												
Start wash-out of phosphate binders	X												
Randomization #1 k					X								
Drug dispense					X	X		X	X	X	X	X	
Drug return						X		X	X	X	X	X	X
Drug accountability l						X		X	X	X	X	X	X
s-Phosphorus i	X	X	X	X	X	X	X	X	X	X	X	X	X
Ca x P, FGF23	X				X					X			X
Exploratory biomarkers	X				X					X			X
AE assessment d	X	X	X	X	X	X	X	X	X	X	X	X	X
Prior/ConMeds	X	X	X	X	X	X	X	X	X	X	X	X	X

Study Day	Randomized Withdrawal Period e							Safety Extension Period			
	183 +7	197 +7	211 +7	225 +7	239 +7	253 +7	267 +7	281 +7	309 +7	337 +7	365 +7
Visit	V13	V14 m	V15	V16 m	V17	V18 m	V19	V20	V21	V22	V23/ EOT
Pre-dialysis Body Weight							X			X	X
KDQoL/DSI f							X				X
Physical Exam							X				X
Vital signs a		X	X	X	X	X	X	X	X	X	X
ECG evaluation							X				X
Clinical laboratory tests b							X				X
Pregnancy test c (serum)							X				X
Randomization #2 k	X										
Drug dispense	X	X	X	X	X	X	X	X	X	X	
Drug return		X	X	X	X	X	X	X	X	X	X
Drug accountability		X	X	X	X	X	X	X	X	X	X
s-Phosphorus i		X	X	X	X	X	X	X	X	X	X
Ca x P, FGF23			X		X		X				X
Exploratory biomarkers			X		X		X				X
AE assessment d	X	X	X	X	X	X	X	X	X	X	X
Prior/ConMeds	X	X	X	X	X	X	X	X	X	X	X

- a Vital signs include blood pressure, pulse and must be performed pre-dialysis.
- b All blood collections are performed pre-dialysis.
- c FSH test and pregnancy test are performed on all females at Screening. After screening, pregnancy tests will only be performed on females of child-bearing potential.

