### 5.1 Inclusion Criteria

A patient will be eligible for study participation if he/she meets the following criteria:

1. Signed and dated informed consent prior to any study specific procedures.
2. Males or females  $\geq$  18 years of age.
3. Females must be non-pregnant, non-lactating and fulfilling one of the following:
  - a. Post –menopausal defined as amenorrhea for at least 12 months following cessation of all exogenous hormonal treatments and with follicle stimulating hormone (FSH) levels in the laboratory defined post-menopausal range.
  - b. Documentation of irreversible surgical sterilization by hysterectomy, bilateral oophorectomy or bilateral salpingectomy, but not tubal ligation.
  - c. Use of acceptable contraceptive method: IUD with spermicide, a female condom with spermicide, contraceptive sponge with spermicide, an intravaginal system (e.g., NuvaRing®), a diaphragm with spermicide, a cervical cap with spermicide, or oral, implantable, transdermal, or injectable contraceptives, sexual abstinence, or a sterile sexual partner.
4. Males must agree to avoid fathering a child (or donating sperm), and therefore be either sterile (documented) or agree to use, from the time of enrollment until 45 days after end of study, one of the following approved methods of contraception: a male condom with spermicide, a sterile sexual partner, use of an IUD with spermicide by female sexual partner, a female condom with spermicide, contraceptive sponge with spermicide, an intravaginal system (e.g., NuvaRing®), a diaphragm with spermicide, a cervical cap with spermicide, or oral, implantable, transdermal, or injectable contraceptives.
5. Chronic maintenance hemodialysis 3x/week for at least 3 months or chronic maintenance peritoneal dialysis (PD) for a minimum of 6 months. If modality of dialysis has changed patient must meet one of the two dialysis criteria above and been on the new modality of dialysis for a minimum of one month.
6. Stable vascular access as assessed by Investigator if on HD.
7.  $Kt/V \geq 1.2$  at most recent measurement prior to screening.
8. Prescribed and taking at least 3 doses of phosphate binder per day. The prescribed dose should have been unchanged during the last 3 weeks prior to screening.

9. Serum phosphorus levels should be between 4.0 and 8.0 mg/dL (inclusive) at screening analyzed at the central laboratory used in the study.
10. Intentionally left blank.

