### 7.3.4 Clinical Laboratory Tests

Samples **must** be obtained, pre-dialysis, for the clinical laboratory tests identified in [Table 7-1](#). A coagulation profile will only be performed on patients taking warfarin.

Other evaluations and tests performed during Screening and other time points, specified in the Schedule of Events ([Section 1.3](#)) will include:

- Serology screen, i.e., HBsAg, HCV, and HIV
- FSH test will be performed on all females at Screening
- Pregnancy test, if applicable

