#### 7.3.6.6 Pregnancy

Female patients must be instructed to discontinue all study drugs and inform the study Investigator immediately if they become pregnant during the study.

The Investigator must report any pregnancy to [REDACTED] within 1 business day of becoming aware of it. The patient must be immediately discontinued from further treatment with study drug. An uncomplicated pregnancy will not be considered an AE or SAE, but all pregnancies will be followed through birth.

Pregnancies are captured if they occur in female patients or in the sexual partners of male patients from the time the patient is first exposed to the investigational product until 30 days after last exposure to the investigational product.

Any congenital abnormalities in the offspring of a patient who received study drug will be reported as an SAE. The outcome of any pregnancy and the presence or absence of any congenital abnormality will be recorded in the source documentation and reported to [REDACTED]

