**8.8 End of 26-week Treatment Period and start of Randomized Withdrawal Period (Day 183 ± 7), Visit 13**

- Randomization #2
- Body weight (pre-dialysis)
- KDQOL survey
- DSI survey (for English speakers only)
- Physical Examination
- Vital signs (pre-dialysis)
- ECG evaluation
- Clinical laboratory tests (pre-dialysis)
- Serum pregnancy test, if applicable
- FGF-23, Ca x P product and exploratory biomarker sample (pre-dialysis)
- Return/accountability of study drug or active control
- Dispense study drug or active control, if applicable
- Adverse event reporting
- Review concurrent medications

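### Minor: read literally, Table 7-1 footnote g drops post-screening pregnancy tests on screening FSH alone, in conflict with Schedule footnote c and inclusion criterion 3a

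*Combined protocol and SAP*

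**What the plan says.** Two footnotes in the protocol state who has a pregnancy test after screening.

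- Schedule of Events (Section 1.3), footnote c: "After screening, pregnancy tests will only be performed on females of child-bearing potential". No further exemption follows.
- Table 7-1, footnote g: "After screening, pregnancy tests will only be performed on females of child-bearing potential unless FSH at screening indicates post-menopausal status".

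Section 5.1 gives three routes by which a woman can qualify.

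- Item 3a, post-menopausal: "amenorrhea for at least 12 months following cessation of all exogenous hormonal treatments and with follicle stimulating hormone (FSH) levels" in the laboratory's post-menopausal range. The Synopsis has the same definition.
- Item 3b, surgical: "Documentation of irreversible surgical sterilization by hysterectomy, bilateral oophorectomy or bilateral salpingectomy, but not tubal ligation".
- Item 3c: an acceptable contraceptive method, abstinence or a sterile partner.

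FSH and serum pregnancy are measured in every woman at screening. At the later visits with a pregnancy test, the procedure lists in Section 8 say only "Serum pregnancy test, if applicable".

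**The concern.** Footnote g starts from the same group as footnote c and then takes some women out of it. The only ground it names is the screening FSH result. It does not cite item 3a or mention amenorrhea. As written, it is looser than the protocol's own definition of post-menopausal, and it gives a different instruction from the Schedule for some women.

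What is at stake is safety monitoring. Section 7.3.6.6 says: "Female patients must be instructed to discontinue all study drugs and inform the study Investigator immediately if they become pregnant during the study". It also requires prompt reporting and follow-up through birth. All of this depends on the pregnancy being detected. For a woman exempted on FSH alone, detection would rest on self-report, adverse-event questioning and observation at visits, routine dialysis checks for hemodialysis patients, or an unscheduled test at the investigator's discretion. None of these is a scheduled pregnancy test, and the same section says that an uncomplicated pregnancy is not an adverse event.

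**Working it through.** The check is mainly a comparison of texts. The plan states no figure to reproduce.

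**Step 1. Classify women by the two limbs of item 3a.**

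| FSH in range | Amenorrhea at least 12 months | Item 3b surgery | Entry route | Footnote c | Footnote g, literal |
|---|---|---|---|---|---|
| Yes | Yes | Either | 3a (or 3b) | Not tested, if 3a or 3b means not of child-bearing potential | Not tested |
| Yes | No | Yes | 3b | Not tested, same proviso | Not tested |
| Yes | No | No | 3c only | Tested, if taken to be of child-bearing potential | **Not tested** |
| No | Either | No | 3c only | Tested, same proviso | Tested, same proviso |

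The footnotes part only in the third row.

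**Step 2. Does the extra clause do any work?** If women meeting 3a are already outside the child-bearing group, the clause is redundant for them. It changes what happens only for a woman otherwise counted as of child-bearing potential, which is the third row.

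**Step 3. Does another section decide between the footnotes?** Section 7.3.4 first refers to Table 7-1 for the standard tests. It then lists the pregnancy test under "Other evaluations and tests performed during Screening and other time points, specified in the Schedule of Events". Table 7-1 footnote e agrees: it puts the column holding the pregnancy test outside the standard panel, to be done at specified times. Both point toward the Schedule. Neither says that the Schedule prevails over footnote g, and the term 'child-bearing potential' is not defined.

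**Step 4. Size for one affected woman who completes the study, on the literal reading.**

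- Visits marked for a pregnancy test in the Schedule: V1, V5, V10, V13, V19, V23 = 6. After screening: 6 − 1 = 5. All five could be omitted.
- V5 is the visit at which drug is first dispensed. Section 4.1 sets the wash-out at 1 to 4 weeks, so her last result would be 1 to 4 weeks old at first dose.
- Nominal time from screening to Day 365: (365 − 1)/7 = 52 weeks, plus 1 to 4 weeks = 53 to 56 weeks with no scheduled test.
- For comparison, if tested as scheduled, the nominal intervals after Day 1 are 85 − 1 = 84, 183 − 85 = 98, 267 − 183 = 84 and 365 − 267 = 98 days. The longest is 98 days.

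**Step 5. Is extra blood needed to test her?** Table 8-1 counts 6 chemistry samples, described as including the serum pregnancy test. That equals the 6 test visits, so no extra draw is needed.

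**The case against.** The best defense is that footnote g is shorthand. The protocol defines post-menopausal once, in item 3a, and sites must already classify each woman under 3a, 3b or 3c to enroll her. Read that way, the clause repeats what footnote c implies and no test is lost. This reading is plausible and may be the intended one. It does not remove the point: the clause names one of the two limbs of the definition and cites neither 3a nor amenorrhea, and a site following the table literally would act on FSH alone.

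It can also be said that Section 7.3.4 and Table 7-1 footnote e lead the reader to the Schedule. That stands as guidance. A reader might infer that nothing else in the protocol bears on the conflict, but these two places do; they fall short of a precedence rule.

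The risk is limited in other ways. Every woman is tested at screening. A woman entering under 3c must satisfy one of its contraceptive options, and Section 5.6 repeats the pregnancy precautions. Section 2.5 describes minimal systemic exposure, with fewer than 1% of more than 3000 plasma samples quantifiable. These facts keep the grade low. They do not make the footnotes agree, and Section 7.3.6.6 still requires study drug to stop in pregnancy.

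A reader might also infer that the protocol abandons pregnancy testing for women who could conceive, or that tests will be missed in a known number of patients. The documents support neither. The loss depends on a literal reading, applies to one narrow group, and cannot be counted.

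**Conclusion.** The point holds as a minor inconsistency in a safety rule. Read literally, Table 7-1 footnote g exempts on FSH alone, Schedule footnote c does not, and item 3a requires amenorrhea as well. No section formally resolves the difference.

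Its size is five of six scheduled tests, including the one before first dose, for a completing woman with FSH in range, under 12 months' amenorrhea and no item 3b surgery. This assumes that a site applies footnote g on FSH alone and that she would otherwise count as of child-bearing potential. The documents give no number for this group, and it may be very small or empty. The primary analysis, power and type I error are untouched.

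**What to change.** Change footnote g only. Either delete its final clause, the one beginning 'unless', so that it reads as footnote c does, or replace that clause with: *unless the patient meets Section 5.1 item 3a (both amenorrhea and FSH) or 3b*. The replacement is somewhat better, because it also tells sites how to treat women meeting 3a or 3b where the protocol leaves child-bearing potential undefined.

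Keep testing at the visits already marked: V5, V10, V13, V19 and V23. The wording should not extend testing to every study visit, since visits with only a phosphorus sample have no pregnancy test in the Table 8-1 count and would need added blood.

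The cost is one clause in one footnote and at most a few more assays on chemistry samples already drawn.

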### 7.3.6 Adverse Events

The Investigator is responsible for ensuring that all staff involved in the study are familiar with the content of this section.

An AE is defined as any untoward medical occurrence in a patient administered a pharmaceutical product during the course of a clinical investigation. An AE can therefore be any unfavorable and unintended sign, symptom, or disease temporally associated with the use of an investigational product, whether or not thought to be related to the investigational product.

Patients will be monitored throughout the study for AEs, from the screening visit through the open label extension period on Day 365. All AEs spontaneously reported by the patient or reported in response to the open question from the study personnel: “Have you had any health problems since the previous visit?”, or revealed by observation will be collected and recorded in the eCRF. When collecting AEs, the recording of diagnoses is preferred (when possible) to recording a list of signs and symptoms. In instances of well-recognized symptoms, they can be recorded as the commonly used diagnosis (e.g., fever, runny nose, and cough can be recorded as “flu”). However, if a diagnosis is known, but there are other signs or symptoms that are not generally part of the diagnosis, the diagnosis and each sign or symptom should be recorded separately.

Adverse events that are identified at the last assessment Visit 23 (or the early termination visit) as specified in the protocol must be recorded on the AE eCRF with the status of the AE noted, and the AE must be followed until AE is resolved or stable. All events that are ongoing at this time will be recorded as ongoing on the eCRF. The procedures specified in [Section 7.3.6.8](#) are to be followed for reporting SAEs.

#### 7.3.6.1 Adverse Events Associated with Change in Stool Form and/or Frequency

Based on tenapanor’s ability to inhibit the absorption of dietary sodium, it is known to alter stool form and frequency in some patients. For a change in stool form and/or frequency to be considered an adverse event the patient must consider the bowel movements to be “bothersome.”

#### 7.3.6.2 Recording Adverse Events

Adverse events are to be recorded on the AE page of the eCRF. Severity will be graded according to the following definitions:

- Mild: The patient experiences awareness of symptoms but these are easily tolerated or managed without specific treatment
- Moderate: The patient experiences discomfort enough to cause interference with usual activity, and/or the condition requires specific treatment

- Severe: The patient is incapacitated with inability to work or do usual activity, and/or the event requires significant treatment measures.

Action taken will be categorized as dose not changed, dose reduced, drug interrupted, drug withdrawn, required concomitant medication, required concomitant procedure and/or other.

Event outcome at resolution or time of last follow-up will be recorded as not recovered/not resolved, recovered/resolved, recovered/resolved with sequelae, recovering/resolving, fatal or unknown.

#### 7.3.6.3 Assessment of Adverse Events

The relationship of the event to the study drug or active control should be determined by the Investigator according to the following criteria:

- Not related: The event is most likely produced by other factors such as the patient's clinical condition, intercurrent illness, or concomitant drugs, and does not follow a known response pattern to the study drug/active control, or the temporal relationship of the event to study drug/active control administration makes a causal relationship unlikely
- Possibly related: The event follows a reasonable temporal sequence from the time of drug administration, and is possibly due to drug administration and cannot be reasonably explained by other factors such as the patient's clinical condition, intercurrent illness, or concomitant drugs.
- Related: The event follows a reasonable temporal sequence from the time of drug administration, and/or follows a known response pattern to the study drug/active control, and cannot be reasonably explained by other factors such as the patient's clinical condition, intercurrent illness, or concomitant drugs.

#### 7.3.6.4 Following Adverse Events

All (both serious and non-serious) AEs must be followed until they are resolved or stabilized, or until all attempts to determine resolution of the event are exhausted. The Investigator should use his/her discretion in ordering additional tests as necessary to monitor the resolution of such events.

#### 7.3.6.5 Discontinuation due to Adverse Events

Any patient who experiences an AE may be withdrawn at any time from the study at the discretion of the Investigator. Patients withdrawn from the study due to an AE, whether serious or non-serious, must be followed by the Investigator until the clinical outcome of the AE is determined. The AE(s) should be noted on the appropriate CRFs and the patient's progress should be followed until the AE is resolved. A decision to discontinue a patient due to an AE should be discussed with the Medical Monitor. If the AE may relate to overdose of

study treatment, the IB should be consulted for details regarding any specific actions to be taken.

#### 7.3.6.6 Pregnancy

Female patients must be instructed to discontinue all study drugs and inform the study Investigator immediately if they become pregnant during the study.

The Investigator must report any pregnancy to [REDACTED] within 1 business day of becoming aware of it. The patient must be immediately discontinued from further treatment with study drug. An uncomplicated pregnancy will not be considered an AE or SAE, but all pregnancies will be followed through birth.

Pregnancies are captured if they occur in female patients or in the sexual partners of male patients from the time the patient is first exposed to the investigational product until 30 days after last exposure to the investigational product.

Any congenital abnormalities in the offspring of a patient who received study drug will be reported as an SAE. The outcome of any pregnancy and the presence or absence of any congenital abnormality will be recorded in the source documentation and reported to [REDACTED]

